#### 3.1.2 Conditional survival

For Primary Endpoint analysis #2 (Conditional survival or CS), survival will only be evaluated for subjects known to have survived to at least the observed median (M months OS) for subjects randomized to DCVax®-L. CS will be calculated from M months after the date of randomization to death due to any cause. If a subject is not known to have died at the date of database lock, the date the subject was last known to be alive will be used to calculate CS and will be considered censored [9].

Published data from other trials include OS at various time points and include Kaplan-Meier (KM) survival curves. The KM curves will be digitized and individual survival data will be derived from the digitized KM curves. In addition, access may be obtained to original data sets from some other trials. CS for subjects randomized to DCVax®-L in the Trial who survived to at least the observed median will be compared to matched external controls comprised of subjects who survived to at least the same time point (M months) in the other trials which have been selected by independent experts, confirmed with independent neuro-oncology experts and further matched through MAIC, pursuant to this SAP to serve as the comparison trials.

cPFS for subjects randomized to DCVax®-L will be compared to within-Study controls (i.e. subjects randomized to placebo).

#### 3.1.3 Confirmed progression-free survival

Confirmed PFS (cPFS) will be measured from the date of randomization to the date of confirmed progressive disease (cPD; see section 1.2.2, Appendix C) or death. An initial determination of

progression will be made in the same manner as for PFS (see sections 1.2.2, 3.1.4 and Appendix C): these events will for this analysis be qualified as 'unconfirmed progression' (uPD) events.

Subsequent review of these events will then determine whether they can be confirmed, or not, and only events that are subsequently determined to be confirmed progression will be counted as events for the cPFS endpoint. Events initially classified as uPD which are not subsequently confirmed will be censored.

cPFS for subjects randomized to DCVax®-L will be compared to cPFS for withhin-Study controls (i.e. subjects randomized to placebo).

#### 3.1.4 Progression-free survival

PFS is defined as the time from randomization until objective demonstration of tumor progression or death, whichever occurs first [10]. If neither tumor progression nor death are known to have occurred by the date of database lock, the date the subject was last known to be alive and progression-free will be used to calculate PFS, which will be considered censored.

When data points, especially in regards to radiographic imaging data, are missing, strong efforts will be made to obtain the missing study information. In spite of these efforts, there may be missing data regarding assignment of primary and secondary endpoints. Detailed rules for the definition of progression-free survival (modified Macdonald criteria) are provided in Appendix C.

Within-Study controls are used for this endpoint.

#### 3.1.5 Time to progression

Time to progression (TTP) is defined as the time from randomization to disease progression (per modified Macdonald criteria determined by independent ICON Medical Imaging review). For patients who die before experiencing progression, TTP will be censored at the date of death. Within-Study controls are used for this endpoint.

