#### 8.4.3 Time to progression (TTP)

Time to progression (TTP) is defined as the time from randomization to disease progression (per modified Macdonald criteria determined by independent ICON Medical Imaging review).

Progression is censored when a uuPD occurs. For patients who die before experiencing progression or uuPD, progression is censored at death. Within-Study controls are used for this endpoint.

TTP will be analyzed using a cause-specific Cox proportional hazards regression model [31].

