## **APPENDIX C: Progression-free survival**

Situation	Date of Progression or Censoring	Outcome
Progression documented between scheduled visits	Actual date of documented progression	Progression
No progression	Date of last radiology assessment demonstrating no progression	Censored
Treatment discontinuation for undocumented progression	Date of last radiology assessment demonstrating no progression	Censored
Treatment discontinuation for toxicity or other reason	Date of last radiology assessment demonstrating no progression	Censored
New anticancer treatment started	Date of last radiology assessment demonstrating no progression	Censored
Progression after more than one missed visit	Date of last radiology assessment demonstrating no progression	Censored
Death before first PD assessment	Date of death	Progression
Death between adequate assessment visits	Date of death	Progression
Death after one or two missed visits (≤ 4 months from last MRI)	Date of death	Progression
Death after more than two missed visits (> 4 months from last MRI)	Date of last radiology assessment demonstrating no progression	Censored
No MRI post baseline and no death within 4 months of baseline and withdrawn from study	Date of withdrawal	Censored

In practice, this is executed as follows:

Take the minimum of the following dates

- Confirmed Progression
- Death
- Withdrawal due to reason "OTHER", "DISEASE PROGRESSION" or "PATIENT ENROLLED IN A TRIAL OF ANOTHER INVESTIGATIONAL AGENT FOR THE TREATMENT OF GBM"

Depending on which of these dates is the minimum decides how PFS is calculated. It is possible that all three of these dates are missing for a patient and therefore they have no minimum date. When two different dates are both the minimum date and it needs to be decided which set of rules to follow then the rules are picked using priority Confirmed Progression > Death > Withdrawal.

e.g. a patient has a confirmed progression and a withdrawal on the same day, both of which occur before death. Use the Confirmed progression rule to derive PFS because Confirmed Progression > Withdrawal.

Minimum Date	Rule to determine PFS date and censoring		
Confirmed Progression	
 
If their last MRI prior to progression was within 4.5 months of their progression, then use confirmed progression date, uncensored
 
Otherwise use previous MRI, censored
 
		

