Death	
 
If subject died within 2 months of randomization, use date of death, uncensored
 
If the subject died within 4.5 months of an MRI scan use date of death, uncensored
 
Otherwise use previous MRI, censored
 
		
Withdrawal due to one of the specified reasons	Use last MRI prior to withdrawal, censored		
No minimum date	Use the last MRI, censored		

In the above table there are various conditions which require to use the last MRI as the PFS date. However there are cases when the subject either does not have MRI data or the last MRI was pre baseline. In these cases use the date of study completion, censored.

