#### 3.1.3. Tertiary objectives

- To compare immune responses between patients in the treatment cohort and patients in the placebo cohort for all randomized patients (i.e., patients randomized at baseline with no evidence of disease progression); The percentage of patients mounting a T cell response to tumor antigens is expected to be higher in patients immunized with DCVax-L when compared to patients immunized with the placebo;
- To compare decline in physical functioning, measured by KPS evaluation, between patients in the treatment cohort and patients in the placebo cohort for all randomized patients (i.e., patients randomized at baseline with no evidence of disease progression). Patients in the treatment cohort are expected to experience a slower rate of decline in physical functioning than patients in the placebo cohort.;

Protocol: 020221, v7.0 23SEP2020 Page 11 of 55

- To compare time to progression of disease (TTP; includes as events all radiographic evidence of disease progression; all deaths are censored) between patients in the treatment cohort and patients in the placebo cohort for all randomized patients (i.e., patients randomized at baseline with no evidence of disease progression). TTP is expected to be longer for patients in the treatment cohort than for patients in the placebo cohort.;
- To compare survival at 6, 12, 18, 24, 36 and 48 months between patients in the treatment cohort and patients in the placebo cohort for all randomized patients (i.e., patients randomized at baseline with no evidence of disease progression). The percentage of patients surviving at these time points is expected to be greater in the treatment cohort than in the placebo cohort.

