#### 11. PATIENT DISCONTINUATION OF ACTIVE TREATMENT

An explanation for discontinuing treatment is recorded for each patient discontinuing treatment on the appropriate CRF/eCRF. The Sponsor, or its designee, must be notified immediately if a patient discontinues treatment. All patients, irrespective of treatment status, will continue to be followed for survival. Treatment in this study must be discontinued for any of the following reasons:

- if the Sponsor decides to stop the study;
- at Investigator's discretion;
- at the patient's request;
- if the patient enrolls in a trial of another investigational agent for the treatment of GBM;
- Grade 4 or life-threatening toxicity (See Section 11, Adverse Events) attributable to DCVax-L:
- injection site reactions of Grade 3 or higher, according to the grading in Appendix E, Modified Grading of Injection Site Reaction Toxicity;
- development of clinical signs and symptoms of autoimmune disease;
- pregnancy;

development of an allergic reaction of Grade 2 or higher, with exception of transient (<1 hour) fever or other constitutional symptoms, localized urticaria, and transient (<30 seconds) shortness of breath, or immunological reaction Grade 3 or higher to DCVax-L, with the exception of low grade fever of <39°C (102.2°F) which resolves spontaneously or with antipyretics within 48 hours.

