## 15.2. DEFINITION OF PROGRESSION AFTER ENROLLMENT

Progression, calculated from the nadir tumor burden (i.e. post operative orBaseline), is defined as one of the following:

- In the case of complete resection during primary therapy: a new measurable tumor at
  the site of the resected tumor, defined as a mass with a longest diameter equal to or
  greater than 1 cm in at least one dimension. If progression is not defined by these
  studies, treatment may proceed and determinations made at the next scheduled MRI.
- In the case of incomplete resection during primary therapy: a 25% increase or greater
  in the residual tumor if the recurrent portion of the tumor is at least 1 cm or greater in
  its longest diameter, measured by MRI and confirmed by scans above as attributable
  to tumor growth;
- If resection is indicated for recurrent disease, while radiographic criteria for progression have not been met: surgical resection, subsequently confirmed as

progressive GBM by Pathology at the clinical site and to be confirmed by independent pathology;

- Appearance of any new lesion/site at least 1 cm in at least one dimension or greater measured by MRI and confirmed by scans above;
- Unequivocal progression of non-measurable disease (either non-enhancing disease seen only on T2/FLAIR images or enhancing disease not meeting size criteria for measurability), such that there is confidence that tumor growth has occurred;
- Death: all deaths are counted as events for the primary endpoint.

Radiographic evidence of disease progression will be evaluated and corroborated by independent radiology review to determine disease progression for purpose of this trial. MRIs to assess disease progression are done every 2 months. Unscheduled MRIs or other testing will be recorded in CRFs/eCRFs. If, during unscheduled procedures, there is evidence of disease progression, it must be confirmed through independent review as described above.

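### Exploratory TTP is censored at death however old the last MRI is, so unscanned months count as progression-free; Appendix C does not allow this for PFS after a long scan gap

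*Combined protocol and SAP*

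**What the plan says.** **TTP.** SAP 3.1.5 measures TTP from randomization to progression as read by independent imaging review. For deaths: "For patients who die before experiencing progression, TTP will be censored at the date of death". SAP 8.4.3 adds censoring at ultimately unconfirmed progression (uuPD), which 3.1.5 omits, and otherwise agrees: "For patients who die before experiencing progression or uuPD, progression is censored at death". The model is stated as: "TTP will be analyzed using a cause-specific Cox proportional hazards regression model". Protocol v7.0 section 3.1.3 says of TTP that it "includes as events all radiographic evidence of disease progression; all deaths are censored", without giving a censoring date.

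**PFS.** SAP 3.1.3 and 3.1.4 refer cPFS and PFS to Appendix C; 3.1.5 and 8.4.3 do not cite it. The Appendix C situation table has a row beginning "Death after more than two missed visits (> 4 months from last MRI", with censoring at the last radiology assessment that showed no progression. The execution rule counts death as an event if it falls within 4.5 months of an MRI, or within 2 months of randomization. For the remaining deaths it says: "Otherwise use previous MRI, censored".

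**Follow-up.** Protocol 15.2 states: "MRIs to assess disease progression are done every 2 months". Vital status is collected separately from scanning. Protocol section 11 says: "All patients, irrespective of treatment status, will continue to be followed for survival". The Appendix A footnotes describe quarterly phone calls and public record searches, and the Appendix A schedule marks no MRI after month 36.

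**The concern.** A cause-specific Cox model treats time in the risk set as time in which an event could have been observed. A TTP event needs a scan. Once a patient stops scanning, each further month until death adds to the denominator and cannot add an event. The SAP recognises this for PFS, where a long scan gap sends the censoring date back to the last MRI, but it leaves the same months in TTP as progression-free time.

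What is at stake is the TTP curve, the TTP landmark estimates and, if the arms differ in how often patients leave scanning, the TTP hazard ratio. SAP Table 2 lists both hazard ratio and landmarks for TTP. The version measured from surgery (isTTP, SAP 3.2.3) inherits the rule.

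**Working it through.** **1. The plan's own figures.** The SAP gives no event count, power or expected curve for TTP, so there is no TTP figure to reproduce. The PFS design, which supplies the 7-month median used below, does reproduce. Schoenfeld events = (z for one-sided 0.01 + z for 84% power)² / [(1/3)(2/3)(ln 7/11)²] = 243, against 248 stated. Power at 248 events is 84.8%, against 84%. This confirms that the inputs are read correctly; it does not bear on the point.

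**2. One patient under both rules.** Last clean MRI at month 4, death at month 20, no progression recorded. The gap is 20 − 4 = 16 months, beyond both 4 and 4.5. PFS is censored at month 4 and TTP at month 20, so 16 unscanned months are discarded for PFS and counted as progression-free for TTP.

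**3. Effect on the curve (simulation, 200,000 patients per arm, inert treatment).** Assumptions:
- True progression is exponential with median 7 months (SAP Table 1, placebo PFS) and is detected at the next 2-monthly scan.
- Scanning stops at a constant monthly rate, and in any case at month 33 (36 protocol months of 28 days).
- Death comes an exponential time after progression, mean 10.1 months. This puts median OS at about 17 months, the placebo figure in SAP 1.3.2.
- The stopping rates are assumed. The 1% equals the loss-to-follow-up rate in Table 1; the others have no source in the documents.

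| Stopping per month | 24-month share, censored at death | 24-month share, censored at last MRI | Never recorded as progressed |
|---|---|---|---|
| 0.25% | 13% | 11% | 15% |
| 1% | 17% | 11% | 21% |
| 1.5% | 20% | 11% | 25% |
| 3% | 28% | 11% | 34% |

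The true share is 2^(−24/7) = 9%. The step from 9% to 11% comes from deaths between true progression and the next scan, which neither rule records.

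**4. Effect on the hazard ratio, same model (true HR 1.00).**

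| Stopping, DCVax-L / placebo | Censored at death | Censored at last MRI |
|---|---|---|
| 1% / 1% | 1.00 | 1.00 |
| 2% / 1% | 0.88 | 1.00 |
| 1% / 2% | 1.14 | 1.00 |

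The last two rows mirror each other (1/0.88 = 1.14); simulation error is about 0.01.

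**5. A second model.** Here progression, scan-stopping and death after the last scan are all exponential.
- No true effect (median TTP 7 months in both arms, death a median of 17 months after the last scan): death censoring gives 0.99 to 1.02 with equal stopping, 0.79 at 3% DCVax-L / 1% placebo, and 1.30 with the rates reversed.
- True HR of 7/11 = 0.636, equal stopping, death a median of 17 (placebo) or 25.3 (DCVax-L) months after the last scan: death censoring gives 0.67 to 0.68. Last-MRI censoring gives 0.63 to 0.65 across all rates tried.

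**6. If stopping depends on unseen progression.** Let stopping be 1% per month before true progression, then 30% per month in one arm and 10% in the other. With no drug effect, death censoring gives HR 0.77 in favour of the faster-stopping arm, and last-MRI censoring gives 0.85. The bias shrinks but remains.

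**The case against.** **TTP is exploratory.** SAP 1.2.4 and Table 2 place it there. It carries no alpha and gates nothing. This stands.

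**Ending risk time at a competing death is standard in a cause-specific model.** That is true while the patient is still under observation for the event. It does not justify counting months in which the event could not be observed.

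**The contrast with PFS is narrow.** This stands. After a short gap, or for a death within 2 months of randomization, PFS takes the date of death as an event. A reader might infer that Appendix C always goes back to the last MRI; it does so only for the long gaps.

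**Follow-up for progression was promised.** SAP 1.1 and Protocol 3.3 and 15.5 say so. These passages set no scan schedule beyond Appendix A, so gaps remain possible, but their frequency is unknown.

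**The assumed rates may be too high.** Protocol 8.4 ties crossover to independently verified progression, and SAP 1.1 says about 90% of the ITT population crossed over. On that reading only about 10% could lack verified progression, against 21% to 34% in the model at 1% to 3% per month. This favours the lower rates, although the bound is uncertain: SAP 1.2.3 describes the 90% as patients who received DCVax-L, and the model leaves about 13% without recorded progression even with no early stopping. Also, the 1% in Table 1 is general loss to follow-up, and a patient who is truly lost has no recorded death for this rule to act on.

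**Bias in favour of DCVax-L.** A reader might infer that the rule flatters DCVax-L. The documents do not support this. They report no scan-stopping by arm, the plan keeps patients, investigators and sponsor blinded to initial assignment, and the hazard ratio can move either way.

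**Conclusion.** The point holds as an inconsistency in an exploratory endpoint. SAP 3.1.5 and 8.4.3 count unscanned months before death as at risk and progression-free, while Appendix C censors PFS at the last MRI once the gap to death exceeds 4 or 4.5 months. Nothing in the documents applies Appendix C to TTP.

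Under assumed scan-stopping of 0.25% to 1% per month, the 24-month progression-free share is overstated by roughly 2 to 6 percentage points in both arms (about 13% to 17% against about 11%). The higher rates in the table sit less well with the crossover figure. With equal stopping the null hazard ratio stays at 1.00; a shift to 0.88 or 1.14 needs 2% against 1% per month between arms. These sizes rest on assumed rates and exponential times, because the documents give no count of deaths after a long scan gap.

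Two stronger readings fail. The rule does not threaten any primary or secondary conclusion: TTP gates nothing, and PFS and cPFS have their own rules. Nor does last-MRI censoring remove all bias; where patients stop scanning because of unseen progression it only reduces it.

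**What to change.** In SAP 3.1.5 and 8.4.3, replace the death rule with:

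*Subjects without documented progression, including those who die, are censored at the last post-randomization MRI showing no progression, or at the date of the uuPD if earlier; subjects with no post-randomization MRI are censored at randomization (day 1).*

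The last clause is needed because the baseline MRI precedes randomization, so an unqualified last-MRI rule could give a negative time. The uuPD clause brings 3.1.5 into line with 8.4.3. The sentence also supplies a censoring date for patients alive without progression, which the TTP sections lack. Keep death-date censoring as a sensitivity analysis.

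The cost is one sentence in two sections and slightly shorter TTP follow-up. No event is lost, because a TTP event requires a scan. The SAP describes itself as preceding data lock and unblinding; a change at that stage needs no knowledge of outcomes by arm. Reporting, by arm, the time from last MRI to death among patients without recorded progression would show whether the rule matters in practice.

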#### 3.2 Other endpoints

#### 3.2.1 Immunostimulatory response

A subject will be considered a responder if any of the following conditions holds:

- T cell proliferative response to DCVax®-L shows a stimulation index of 2 or greater;
- A greater than 3-fold increase in CD8+ cells staining with tumor antigen tetramers;
- An ELISPOT response exceeding background signal by at least 2 standard deviations. The background signal will be based on the level of response in patients randomized to placebo.

#### 3.2.2 Physical functioning

- Time from date of randomization to a 10-point decline in KPS will calculated.
- Time from date of surgical resection to a 10-point decline in KPS will calculated.

#### 3.2.3 Endpoints measured from surgery

The primary and secondary endpoints will be measured from the time of initial surgery ('is'), in addition to being measured from randomization as described above:

- isOS
- isCS
- isOS sub-groups
- isOS post-progression
- iscPFS
- isPFS
- isTTP

These endpoints are defined the same as for OS, CS, OS (sub-groups), OS (post-progression), cPFS, PFS, OS and TTP but with the time interval measured from initial surgery in place of randomization.

#### 3.2.4 Tumor response

Subjects deemed to be responders (as defined in section 1.2.3) will be identified according to RANO or iRANO criteria, modified per Cloughesy et al. [7].

#### 3.2.5 Ultimately unconfirmed progression

For the cPFS (confirmed PFS) endpoint, events that have been preliminarily identified as disease progression by MRI (uPD events) are classified as cPD events if subsequent scans or medical review demonstrate further progression. The remaining uPD events will be classified as uuPD events, for ultimately unconfirmed disease progression. These uuPD events will by default include events that are not reflective of actual disease progression and will therefore contain a large proportion of the pseudo-progression events, including those induced by DCVax®-L vaccination, that may have occurred in this study.

A KM plot of the percentage of subjects free of uuPD events versus time by treatment arm is intended to aid in the interpretation of the influence of vaccine-induced, pseudo-progression, if any, on the analysis of the primary and secondary endpoints. One example is that an increase incidence in uuPD events over time in the DCVax®-L treatment group relative to the control group could possibly be an indication of the presence of vaccine-induced, pseudo-progression in the analysis of OS, cPFS and PFS.

